Gout affects over 9 million Americans,¹⁻³ is the most common form of inflammatory arthritis in men, and is associated with poor quality of life.⁴⁻⁶ The frequency of gout is increasing worldwide, with prevalence rates estimated to be as high as 7% in older men.^{2, 7, 8} Gout leads to work absenteeism, loss of productivity, increased healthcare utilization, and premature death.⁹⁻¹³ In addition, gout and hyperuricemia are strongly associated with comorbid conditions such as chronic kidney disease, hypertension, cardiovascular disease and metabolic syndrome; conditions endemic in the Southeast.¹⁴ The US National ED Sample (NEDS) reports over 200,000 visits annually with gout as the primary diagnosis, accounting for 0.2% of ED visits and over \$280 million in annual billable charges.¹⁵ In addition, NEDS data demonstrate a marked increase in the number of ED visits in the US for gout, from 168K to 214K between 2006 and 2014, respectively, with more than 1.7 million people being seen in an ED for acute gout.¹⁶ Gout patients are preferentially prescribed opioids in over 50% of ED encounters, potentially attributable to ED physicians de-prioritizing gout management for patients with more severe conditions.¹⁷ Of note, Alabama and Tennessee are both in the top 10 states for opioid use.¹⁸ The UAB EDs see a combined average of 1150 patients/year with gout. Older age, male sex, lower income, and being an African American were associated with increased ED gout visits and greater gout-related expenses.¹⁹⁻²¹ With an aging population that is living longer with more serious chronic comorbid conditions, the societal burden posed by gout is growing exponentially and will substantially burgeon over the coming decades.^{22, 23} Based on this epidemiology, the ED is a natural place to improve gout care. Most patients seen in an ED will be discharged home; many with inadequate follow-up. At the time of initial gout symptoms, patients have accumulated significant deposits of urate leading most to life-long intermittent if not chronic symptoms without treatment; gout is also quite frequently accompanied or preceded by other chronic diseases.²⁴⁻²⁹ For those with comorbid chronic conditions, continuity of care is the cornerstone for improving patient outcomes and reducing healthcare-related costs.³⁰⁻³² Because gout is a chronic condition which develops in the presence of hyperuricemia, achieving low serum urate concentrations long-term is essential for improving outcomes with gout.^{1, 33-36} However, an optimal strategy for gout care relies on a complete understanding of gout prevention, good continuity of care, patient empowerment to actively participate in their medical care, and adherence to treatments, which cannot be optimally achieved in the ED setting.

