
A.2 Clinical informatics to Improve Healthcare

Over the last 20 years clinical decision support tools have been implemented through electronic medical record (EMR) systems as a means to improve care delivery and outcomes for a variety of conditions in busy clinical settings.³⁷⁻⁴¹ In this project, we will develop electronic alerts that operate in both Cerner (North Kansas City, MO) and Epic (Verona, WI) platforms, two of the most commonly used EMRs in the U.S. We will build EMR phenotypes that will trigger best practice alerts (BPAs) based on clinical and demographic data available in real time, and we will test the diagnostic accuracy of these phenotypes to identify ED patients with acute gout flares. When an acute gout flare alert is triggered, clinicians can then activate an evidence-based order set and an ED research assistant can be alerted to further evaluate each patient for possible participation in our interventional study and the Gout CORT Registry and Biorepository.

A.3 Scientific Premise

The premise for this project is the known disparities in gout care, a higher prevalence of gout in the Southeast due to disproportionate endemic obesity and comorbidity burden, lack of gout knowledge/educational resources, and a perceived lack of access/adherence to primary and specialty gout care, which leads to

excessive care delivery in the ED. From prior work in osteoporosis management we have found that stories can influence readiness to behavior change and can act as very likely mediator of follow-up visits for care.^{42, 43} Moreover, UAB has proven expertise both in using the ED as a setting for biomedical research and for conducting innovative research to enhance minority patient recruitment into clinical trials.⁴⁴⁻⁵³ The premise for aim 3 of this study is that minority recruitment is low in most studies throughout the US and, under a collaborative NCATS grant aimed at overcoming some of these barriers, we have developed culturally tailored methods we will disseminate in this proposal. Importantly, the current CORT projects that focus on gout mechanisms, genetics, and precision medicine for improving gout outcomes will be enhanced by this proposal are dependent on sufficient phenotypic, genotypic and other patient data as well as having a diversity of participants to markedly improve their generalizability.

A.4 Storytelling as Method to Improve Chronic Disease Care

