Prior to the start of the study, clinical staff working in the UAB ED will participate in sessions where they will be trained and coached to appropriately use the novel gout alert for acute gout (flare) identification. Training will occur during monthly face-to-face meetings and via electronic communication (email, list-serves, social media and study website, short training videos). Since busy ED physicians and staff may fail to recall the details of the study or its purpose in real time, we will build electronic reminders (gout alerts) to notify staff to potential eligibility of patients during the ED visit. We will also generate monthly reports that document the number of patients with potential acute gout flares and compare to the number of patients approached by the on-call research coordinator located in each ED. De-identified reports will be shared with practicing clinicians to provide feedback on performance. UAB deploy over 200 different types of alerts, including drug interaction alerts from the Cerner and Epic systems, including both standard alerts and custom alerts that may be overridden by the clinician users. For this study, we will implement a custom alert than can be overridden at the point of care for the Epic and Cerner systems to identify emergency patients who may be having a gout flare. Administrative billing codes (ICD 10), medications (e.g. urate lowering therapy (ULT) such as allopurinol) and healthcare resource utilization of participants will be captured using structured data in conjunction with keywords in unstructured fields. Using this approach, we will identify patients with an existing gout diagnosis and those newly diagnosed during the index ED visit with gout when the alert is activated.

B.3.1 NLP Algorithm

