Patients and study coordinators will enter baseline demographic, gout history, patient reported outcomes (PROs) directly into electronic case report forms into a 21CFR and HIPAA compliant REDCap (Nashville, Tennessee) system. We will host REDCap on one of several access-controlled, encrypted servers housed at UAB. Subsequent PROs and other outcome data will be captured by phone in the same REDCap database by the study teams. Baseline laboratory data and medication data will be obtained from our respective EMRs and will be reviewed during the phone calls and by the research assistant during the ED visit.

B.8 Study Outcomes

Study outcomes (**Table 2**) will be collected from patients at 6 weeks and 3 months following the initial ED visit with questionnaires deployed using computer assisted telephone interviews (CATI) programmed in REDCap. Validated items about gout flares and gout medications have been used in the past by our team.⁸⁴

B.8.1 Primary outcomes Aim 1 and 2.

The primary outcome of aim 1 will be the ability of the alert to successfully identify gout patients. For aim 2, it will be the proportion of patients that have a follow-up visit addressing gout in the 3-month period after the ED visit. Many gout patients are not adherent with their follow-up visits due to a lack of awareness of the consequences of untreated

gout, poor care access, and/or inadequate assistance to obtain a follow up visit. Even rapidly-scheduled outpatient visits (next business day) following an ED encounter are only attended by 73% of those seen in a recent study and rates of post-ED follow-up for many chronic disease are closer to 50%.^{91, 92} Moreover, most patients, ~80%, leave the ED with knowledge deficits that impact adherence and outcomes.^{93, 94} Having a usual source of primary care and establishing continuity of care after an ED visit is critical to optimal disease outcomes in all chronic diseases including gout.³⁰⁻³² This data will be captured both by self-report on surveys (this will be the primary study outcome) and by review of EMR data within our respective healthcare systems. While self-report will be impacted by recall and possible social desirability bias, this should be non-differential (bias towards the null).⁹⁵ EMR data will be more accurate for some outcomes but will miss any gout care delivered outside our urban Southeastern medical centers and their satellite facilities.

B.8.1.1 Secondary outcomes - Aim 2

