Outcome ascertainment	X			X	X
Study debriefing				X	
Assess AEs			X	X	X

[°]Primary outcome assessment will occur at any point upto 6 weeks post ED visit dependent on routine care visit; # For individuals randomized to navigation arm; ^{\$}Navigator will contact participant in the week prior to scheduled follow-up visit

B.9.1.6 **Blinding and Unblinding**

Participants will blinded to study assignment at enrollment, and following primary outcome ascertainment will be debriefed regarding the study and its purpose/goals.

B.10 Statistical Analysis Plan

B.10.1 Primary Outcome Analysis - Aim 1.

All analyses will adhere to the principles of rigor, reproducibility and transparency.^{109, 110} To determine the effectiveness of our alert system, we will examine the diagnostic properties (sensitivity/specificity) of the EMR alerts against a gold standard of NLP/ML detection (section C.4.2)

B.10.2 Primary Outcome Analysis- Aim 2.

Descriptive statistics, including measures of central tendency (means for continuous, proportions for categorical) and dispersion (variance, interquartile range) will summarize the distribution of baseline characteristics of randomized patients seen in both EDs. Descriptive statistics will be summarized by treatment arm as well as enrollment site. These statistics will inform the successfulness of randomization in creating comparable groups and ascertain our success in recruiting the populations we seek to target (particularly under-represented minorities). We also will compare the descriptive characteristics between those participants who do and don't respond to follow-up surveys to detect and report any evidence of a selective non-response bias. The primary analysis approach for testing treatment effect will be a multivariable logistic regression

model. We have chosen multivariable logistic regression over Cochran-Mantel-Haenszel approaches to allow for effect estimation of multiple covariates (race, gender, age) upon the primary outcome and to allow tests of interactions. Logistic regression models, including interaction terms, will be developed for 6 week outcomes and 3 month outcomes. We will examine the significance of the effects of the intervention as the outcome of persons receiving at least one outpatient gout follow-up visit at 3 months. We will analyze rates on an intent-to-treat basis for the primary analysis. We will conduct all analyses using SAS 9.4 (Cary, NC)

[figure not shown]

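### Aim 1 plans sensitivity and specificity but no positive predictive value, so it will not show what share of gout alerts are true flares

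*Combined protocol and SAP*

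**What the plan says.** B.8.1 defines the Aim 1 primary outcome as "the ability of the alert to successfully identify gout patients", without a measure or a threshold. B.10.1, which sets out to determine how effective the alert is, says "we will examine the diagnostic properties (sensitivity/specificity) of the EMR alerts" and names NLP/ML detection as the reference standard. A.2 makes the target more specific: "we will test the diagnostic accuracy of these phenotypes to identify ED patients with acute gout flares".

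Other sections bear on the point:

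- **A.1** gives a national frequency: "visits annually with gout as the primary diagnosis, accounting for 0.2% of ED visits".
- **B.3** describes an alert that clinicians can override, in an ED whose staff are busy and whose systems already run more than 200 alert types. Monthly reports count potential flares and "compare to the number of patients approached by the on-call research coordinator located in each ED".
- **B.3.1** develops the rule on a gout-enriched cohort until performance is acceptable, which is not defined. The rule then goes to other sites.
- **B.3.2** plans a review of 100 charts with a gout ICD-10 code and 50 charts without one in which the alert fired. Two rheumatologists confirm the diagnosis and a third settles disagreements.
- **B.11** expects the alert to find about 60% of the gout patients seen at UAB, counting primary and secondary diagnoses, and expects 80% of physicians to respond to it.

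**The concern.** Sensitivity is the share of true flares that the alert catches. Specificity is the share of patients without a flare for whom it stays silent. Neither says how often a fired alert is right, and that is what the clinician and the research coordinator meet in practice. When the condition is rare, patients without it outnumber those with it so heavily that a small false-positive rate can produce more false alerts than true ones.

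This alert is meant for live use and for transfer to other sites. If B.10.1 is followed as written, Aim 1 could report a reassuring pair of figures while the false-alert burden stays unknown. That burden plausibly affects whether physicians keep responding, which the recruitment estimate in B.11 depends on.

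**Working it through.** **The plan's own figure.** The document states no accuracy target for Aim 1. The nearest figure is the expected yield in B.11: (720 + 450) × 0.60 = 1,170 × 0.60 = 702, as stated. The 60% is used below as a stand-in for sensitivity. It is a recruitment assumption, not a measured value.

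**Inputs**

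- Prevalence p = 0.2% (A.1; national, primary diagnosis). An assumed 1% is shown for contrast.
- Sensitivity Se = 60% (B.11), with 90% as an assumed upper value.
- Specificity Sp = 95%, 99% and 99.9%. All three are assumptions, because the document gives none.

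**Formula.** PPV = Se·p / [Se·p + (1 − Sp)(1 − p)]. Alerts per true case = 1 / PPV.

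| p | Se | Sp (assumed) | Calculation | PPV | Alerts per true case |
|---|---|---|---|---|---|
| 0.2% | 60% | 95% | 0.0012 / (0.0012 + 0.0499) | 2.3% | 43 |
| 0.2% | 90% | 95% | 0.0018 / (0.0018 + 0.0499) | 3.5% | 29 |
| 0.2% | 60% | 99% | 0.0012 / (0.0012 + 0.00998) | 10.7% | 9.3 |
| 0.2% | 90% | 99% | 0.0018 / (0.0018 + 0.00998) | 15.3% | 6.5 |
| 0.2% | 60% | 99.9% | 0.0012 / (0.0012 + 0.000998) | 54.6% | 1.8 |
| 0.2% | 90% | 99.9% | 0.0018 / (0.0018 + 0.000998) | 64.3% | 1.6 |
| 1% (assumed) | 60% | 99% | 0.006 / (0.006 + 0.0099) | 37.7% | 2.7 |

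A PPV of 50% requires 1 − Sp = Se·p / (1 − p). At p = 0.2% this is 0.0012 / 0.998 = 0.0012 for Se 60% and 0.0018 / 0.998 = 0.0018 for Se 90%. Specificity would have to be about 99.9% or 99.8%. Differences that look trivial on the specificity scale therefore decide whether most alerts are true or false.

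**What the B.3.2 sample can give**

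- *Coded charts (100).* Once alert status is recorded for each, they give the share of true flares among the alert-positive coded charts.
- *Uncoded charts (50).* All are alert-positive, so they give the share of true flares among uncoded alerts. There are no alert-negative uncoded charts, so specificity for uncoded patients cannot be estimated.
- *Overall.* The 100:50 mix is fixed by design, so a pooled raw proportion is not the PPV in use. With A_c and A_u the EMR counts of alerts in coded and uncoded patients, PPV = (A_c·PPV_c + A_u·PPV_u) / (A_c + A_u).
- *Precision.* With 50 uncoded alerts, the 95% half-width is at most 1.96 × √(0.5 × 0.5 / 50) = 0.139, or about 14 percentage points.

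**The case against.** The strongest reply is that the plan is not blind to false alerts. Sensitivity speaks directly to whether the alert finds gout patients. B.3.2 sends 50 alert-positive uncoded charts to expert review, with a category for other diagnoses. Release to other sites waits for acceptable performance, clinicians can override the alert, and research assistants check eligibility before randomization. All of this is correct. It means that part of the Aim 1 question is answered and that much of the needed data will exist. It does not close the gap, because B.10.1 turns none of it into an estimate of how often an alert is right.

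The reply is also right about the size. A reader might infer that about nine in ten alerts will be false. The documents do not support that: it needs a specificity near 98–99%, which they never state, and at 99.9% most alerts would be true. The 0.2% is a national primary-diagnosis share, whereas the 60% refers to UAB patients with primary or secondary diagnoses. UAB's total ED volume is not given, so the local frequency cannot be derived.

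A reader might also infer that a live PPV is already available at every site. B.9.1.1 places research assistants only in the UAB ED. The monthly reports in B.3 compare potential flares with patients approached, not alerts with confirmed flares. Nothing says that flare status is recorded for every alert. Physicians may also filter which alerted patients reach the coordinator, which could inflate a bedside PPV.

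**Conclusion.** The concern holds in limited form. Aim 1 is incompletely answered, not unanswered: the planned measures leave out the share of alerts that are true flares. At 0.2% that share could lie anywhere from about 2% to 64% over the combinations shown, and at an assumed 1% with 60%/99% it is 38%. These figures illustrate why PPV must be measured; they do not forecast this alert. They rest on assumed specificities, on a national frequency that may differ from that of flares in the study EDs, and on a recruitment yield used as sensitivity.

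It would go too far to say that a mostly false alert would be declared successful and passed on. Acceptable performance is undefined, and no section says that a specificity of 95–99% would be enough. Aim 2 is not affected.

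**What to change.** In B.10.1:

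1. Add PPV for acute gout flare with a 95% confidence interval, and alerts per true flare, as reported Aim 1 measures. They need not be co-primary.
2. Take both from the rheumatologist-adjudicated alert-positive charts in B.3.2. Report them separately for gout-coded and uncoded charts, then combined with weights equal to the EMR counts of alerts in each stratum. Record whether the alert fires on each of the 100 coded charts.
3. State that specificity is not estimable for uncoded patients from this sample.
4. Report a live PPV from research-assistant assessments only as supportive, and only where flare status is recorded. Give the share of alerts not assessed, and caution that physician referral may inflate the figure.

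The cost is a little more analysis and a count of alerts by stratum. The interval will be wide in the uncoded stratum, which has only 50 charts, and the result may look less favourable than sensitivity and specificity alone. Randomization, treatment and Aim 2 do not change.

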- 1) *Gout medical care*- Self-reported flare rates will be captured using the Gaffo gout flare criteria (developed and validated at UAB) and adapted to self-report.^{79, 84} Uptake of evidence-based gout care will include self-reported prescribing rates of ULT and opioid analgesics. We also will determine medication adherence based on participant self-report. Since obesity is a major factor associated with gout and weight reduction will be addressed in the stories (as well as how to avoid foods high in purines), we will examine changes in self-reported weight between study entry and follow-up.
- 2) *Healthcare resource utilization*- outcomes will include repeat ED visits (ED recidivism) and re-hospitalization rates. Outpatient visits to primary care and/or rheumatologists will be measured as the primary outcomes.
- 3) *Health-related Quality of Life (HRQL), Shared Decision Making and Perception* – HRQL will be recorded using the European Quality of Life (EQ-5D) scale⁸⁶⁻⁸⁸. We will use the CollaboRATE scale, a brief patient survey focused on shared decision making, to measure perception of shared decision making from a patient perspective.⁹⁰

B.8.1.2 Key Covariates Aim 2. To better describe the population we are studying and to adjust for any potential imbalances that might not be addressed by randomization, we will collect key social determinants of health as covariates at baseline and for dynamic measures, again at month 3. These will include: health literacy,¹⁰³ economic factors, transportation, discrimination and other key demographics such as educational level, community social economic status, and personal measure of socioeconomic status will be assessed using measures from the Behavioral Risk Factor Surveillance System.¹⁰⁸ We will also capture the time of “stories” watched as a measure of dose-response of the intervention.

B.9 Study procedures and Assessments

B.9.1.1 Screening, Enrollment, and Randomization (see Step-By-Step Guide in Appendix)

Following the gout alert activation in the ED, research assistants housed in the UAB ED will interview patients in person to further determine possible eligibility, and if potentially eligible, to consider randomization. Patients classified as having acute gout based on the Gaffo criteria who meet the inclusion/exclusion criteria will be

Table 2. Specific Aim 2 Outcomes and Covariates

	ED	WK 6	Mo 3	Time Point
Primary Outcome				
Outpatient primary care or specialist visits targeted for gout*		X	X	

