The navigator will conduct two additional follow-up calls at approximately one month (4 weeks) and in the week (anticipated) prior to their visit to confirm the appointment time, the level of support needed (as needs may have changed), and encourage him/her to keep their appointment. In the unlikely event that the appointment with the PCP/gout specialist is sooner than one month, this one-month pre-appointment call will be eliminated and the navigator will have only two calls with the patient.

B.9.1.3 *6 Week Follow-up Assessment*

At 6 weeks following ED visit, participants will be contacted by the Coordinating Center (CC) to to assess project outcomes via a telephone survey. The following information will be collected, and data collected via the surveys and EMR. Following completion of the follow-up surveys the study coordinator will inform and debrief the patient that they participated in a study evaluating methods to improve continuity of gout care. The debrief will be conducted after the 1st survey. If RA the coordinator is unable to reach participant on the phone, the survey questions used to collect the primary outcomes will be sent via email or text messaging using Mosio, which is an HIPAA-compliant application.

- Survey assessments
 - Patient satisfaction
 - HRQL
 - PROs
- Updated medical history and review of concomitant medications
- Assessment of Adverse Events (AEs) (as meeting NIH definition of Phase III study AEs will be collected)

B.9.1.4 *3 Month Follow-up Assessment*

At 3 months (anticipated) post ED visit participants will be contacted to complete a second follow-up survey and end of study (EOS) via telephone to assess secondary outcomes (e.g. adherence to orders, medication RX, and labs (if ordered)).

- Survey assessments
 - Patient satisfaction
 - HRQL
 - PROs
- Updated medical history and review of concomitant medications
- Assessment of Adverse Events (AEs) (as meeting NIH definition of Phase III study AEs will be collected)

B.9.1.5 **Table 1 Visit Schedule**

Visit description / Study procedures	Screening and Enrollment (ED)	V1 (phone)	V2 (phone)	V3	V4 EOS
	Day 0	72 Hours	4 WK	6 WK [°]	3 MO
Review of Inclusion/exclusion criteria following alert notification	X				
Informed consent for INSIGHT Registry	X				
Medical history	X				
Laboratory					
SUA	X				
Sample banking	X				
Randomization	X				
Patient Navigator Contact#		X	X ^{\$}	X ^{\$}	
Updated medical history and concomitant medications		X	X	X	X

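### The primary logistic model for Aim 2 leaves out site; adding it to a main-effects test at 3 months costs almost nothing and gains a little power if sites differ

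*Combined protocol and SAP*

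**What the plan says.** B.10.2 chooses multivariable logistic regression over a stratified test "to allow for effect estimation of multiple covariates (race, gender, age) upon the primary outcome and to allow tests of interactions". It continues: "Logistic regression models, including interaction terms, will be developed for 6 week outcomes and 3 month outcomes". The interactions are not listed. The significance test is attached to "at least one outpatient gout follow-up visit at 3 months", by intention to treat.

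In B.10.2 site appears only in the summaries: "Descriptive statistics will be summarized by treatment arm as well as enrollment site". B.10.3 uses it again in contrasts among the four sites, under secondary analyses. B.8.1.2 collects social determinants partly "to adjust for any potential imbalances that might not be addressed by randomization" and does not say whether they enter the primary model.

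B.9.1.1 randomises 2:1 with race/ethnicity as the only stratum. Section D expects about 168 patients at UAB and 112 from three other centres. Its opening sentence still names two centres, but its list, its enrolment split, B.1 and B.10.3 all have four, so four is used here.

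On timing, B.8.1 defines the primary outcome as "the proportion of patients that have a follow-up visit addressing gout in the 3-month period after the ED visit", and B.11 is also written for 3 months. The footnote to the visit schedule in B.9.1.5 says "Primary outcome assessment will occur at any point upto 6 weeks post ED visit dependent on routine care visit". B.9.1.4 has patients contacted at 3 months to "complete a second follow-up survey and end of study (EOS) via telephone to assess secondary outcomes".

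**The concern.** Whether a patient attends a gout visit plausibly depends on which ED discharged them, through local referral routes and clinic access. Site is known at randomisation but is neither a stratum nor a named covariate. At a non-UAB site the treated share of analysed patients could range by chance from about 48% to 83% (simulated 95% range) around the target of 67%. Leaving a strong predictor out of a logistic model also pulls the treatment odds ratio towards 1, which costs some power.

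The open interaction list leaves unwritten which coefficient is the primary test. Taken alone that is missing detail, and the same edit closes it.

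**Working it through.** **1. The plan's own power (B.11).** Inputs: 200 patients, 2:1 (133 vs 67), control 30%, relative risk 1.68 (treated 50.4%), two-sided 0.05.

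- Pooled proportion = (67 × 0.300 + 133 × 0.504)/200 = 0.436
- Null SE = √[0.436 × 0.564 × (1/67 + 1/133)] = 0.0743
- Alternative SE = √(0.300 × 0.700/67 + 0.504 × 0.496/133) = 0.0708
- Power = Φ[(0.204 − 1.96 × 0.0743)/0.0708] = Φ(0.82) = 79.5%

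The stated 80% is reproduced. It is power for one overall comparison of two proportions.

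**2. Assumptions for the simulations.** From the documents: 200 analysed, 2:1 within race, 60% at UAB (168/280). Not in the documents: race split 60/40, sex split 70/30, the other three sites equal (13.3% each), the site control rates, a common odds ratio across sites, and no effect of race, sex or age on the outcome. The test is the Wald test of treatment with race, age and sex, without and with a four-level site term.

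**3. What a common odds ratio means overall.** The 30% vs 50.4% of B.11 is an odds ratio of (0.504/0.496)/(0.300/0.700) = 2.37. Applying 2.37 at every site:

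- Control rates 30/20/40/50% (UAB first): overall control = 0.6 × 0.30 + 0.133 × (0.20 + 0.40 + 0.50) = 0.327. Treated rates are 50.4/37.2/61.2/70.3%, overall 0.527. Relative risk = 0.527/0.327 = 1.61.
- Control rates 20/40/50/60%: overall control = 0.6 × 0.20 + 0.133 × 1.50 = 0.320. Treated rates are 37.2/61.2/70.3/78.0%, overall 0.503. Relative risk = 0.503/0.320 = 1.57.

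Holding the odds ratio at 2.37 therefore simulates a smaller effect than B.11 plans for. To reach 1.68, the treated rates must be 1.68 × 0.327 = 0.549 and 1.68 × 0.320 = 0.538.

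**4. Power without and with site.** Ranges show where separate simulation sets differ.

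| Site control rates | Effect | Without site | With site |
|---|---|---|---|
| all 30% | RR 1.68 | 79-80% | 79-80% |
| all 40% | RR 1.68 | 95.9% | 95.7% |
| 30/20/40/50% | RR 1.68 | about 85% | about 86% |
| 20/40/50/60% | RR 1.68 | 83-85% | 87-88% |
| 30/20/40/50% | OR 2.37 (RR 1.61) | 77-78% | 78-79% |
| 20/40/50/60% | OR 2.37 (RR 1.57) | 69% | 74% |

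The unequal rows at RR 1.68 exceed 80% because the overall control rate there is 32-33%. The formula in step 1 gives 85.4% for 0.327 vs 0.549 and 84.0% for 0.320 vs 0.538. Only the contrast within a row measures the value of site. With the overall rates held at 30% vs 50.4%, a between-site standard deviation of 0.5 on the log-odds scale gave 79.7% vs 82.2%; a very wide 1.0 gave 79.0% vs 84.7%.

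**5. Type I error.** In 10,000 trials per scenario: 4.9-5.4% without site, 5.1-5.5% with. In sets of 4,000 (Monte Carlo SE about 0.35 points): 4.8-6.1% and 5.1-6.4%.

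**6. Where the gain comes from.** For 20/40/50/60% at odds ratio 2.37, adding site raises the standard error of the treatment coefficient from 0.319 to 0.349, while the log-odds ratio moves from 0.78 to 0.89. The ratio goes from 0.78/0.319 = 2.45 to 0.89/0.349 = 2.55. The conditional estimate lies further from zero; it is not more precise.

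**7. Sparse sites.** Analysed patients outside UAB: 112 × 200/280 = 80, or about 27 per site and 9 controls each if split evenly. A whole site with all or no visits, which would break the site term, arose in 0.0-0.3% of simulated trials.

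**The case against.** The strongest reply is that nothing is broken. Type I error is near 5% without site, and in both unequal scenarios the model without site keeps more than 80% power at a relative risk of 1.68. The benefit rests on site rates that the documents do not give. B.10.2 already puts the significance test at 3 months by intention to treat. B.10.3 names sex, age and race/ethnicity as effect modifiers under secondary analyses, so the likely candidates for interaction can be inferred. All of this stands, and it limits the point to an efficiency improvement.

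Three further objections also stand:

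- A reader might infer from the 69% row that leaving out site costs ten points of the planned power. It does not: that row has an overall relative risk of 1.57.
- A reader might expect adjustment to shrink the standard error. It rises (step 6), and the reported odds ratio changes meaning, while B.11 is written as a relative risk.
- A site main effect does not deal with differing intervention packages. B.9.1.1 describes storytelling with or without navigation and assigns navigators at UAB, whereas D.2 lists navigation at all four sites. Those statements need their own reconciliation, and the simulations assume a common odds ratio.

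What remains is the imbalance between cost and gain. Site is already recorded; including it costs at most about 0.5 points if sites are alike and gains power if they are not.

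**Conclusion.** The point holds as an inexpensive improvement that should be made, with medium confidence. At the planned relative risk of 1.68, adding site gains about 1 to 4 power points in the two unequal-site scenarios, more if sites differ still further, and costs at most about 0.5 points if they do not differ. These sizes depend on the assumptions in step 2, above all the site rates.

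Two stronger readings are not supported. The primary test is not invalid without site, because type I error is near 5% either way. Nor do the documents make a subgroup coefficient the primary test: B.8.1, B.10.2 and B.11 all point to one overall effect at 3 months, and no section proposes otherwise. Interaction terms do no harm in themselves; a centred treatment-by-race term left power at 79.6% with control at 30%.

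The timing conflict is real but separate. The B.9.1.5 footnote and B.9.1.4 cannot both stand beside a 3-month primary outcome.

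**What to change.** - In B.10.2, define the primary test as the treatment coefficient at 3 months in a main-effects logistic model with race/ethnicity, four-level site, age and sex, and close that list in advance.
- State a rule for pooling the non-UAB sites, for example if any site has all or no visits.
- Report a standardised risk ratio beside the site-conditional odds ratio, to match B.11.
- Move named treatment-by-covariate terms and the 6-week model to secondary analyses, and the B.8.1.2 social determinants to a sensitivity model.
- Separately, reconcile the B.9.1.5 footnote and B.9.1.4 with the 3-month primary outcome in B.8.1, B.10.2 and B.11.

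The cost is SAP wording and a few lines of SAS, with no new data or patients. The statistical price is up to three degrees of freedom and an odds ratio that is now conditional on site.
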